1.2 Preclinical Data

To support the topical ocular administration of H-1337 in humans, a series of nonclinical toxicology and safety pharmacology studies with topical and systemic dosing of H-1337 were conducted. These studies included GLP 4-week studies in rabbit and monkey using the topical/ocular mode of administration which evaluated the potential H-1337 to cause toxicity to the eye and surrounding ocular tissues as well as the potential for H-1337 to cause systemic toxicity. To more comprehensively characterize the systemic safety profile of H-1337 in the event of significant absorption from the ocular into the systemic or non-ocular peripheral tissue compartments, a comprehensive series of studies were conducted utilizing parenteral or oral routes of administration. The core battery of safety pharmacology studies included a neuropharmacology study and a pulmonary function study in rats as well as a cardiovascular study in conscious telemetered monkeys.

Overall, the concern for potential adverse effects is largely mitigated by the very large safety margins between the doses associated with systemic effects in animals and the proposed human clinical doses/concentrations to be administered topically.

The effects defined in nonclinical toxicology and safety pharmacology studies conducted with H-1337 following topical ocular administration in the proposed formulation support the doses proposed for clinical evaluation. Given the collective nonclinical data and the low systemic levels post topical ocular administration of H-1337, systemic effects are considered unlikely following topical ocular administration in humans.

For complete information on the preclinical studies performed, please see the Investigator's Brochure.

1.3 Risk/Benefits

H-1337 is a new drug and has not yet been evaluated in humans. While H-1337 is a new drug being tested for the first time in humans, other kinase inhibitors have been associated with conjunctival hyperemia and, in some instances, conjunctival hemorrhage. Transient conjunctival hyperemia has been noted in preclinical studies of H-1337. Additional adverse effects could include signs and symptoms associated with ocular irritation.

The potential benefit to humans will be the IOP-lowering capabilities via a new mechanism that affects the trabecular meshwork and conventional outflow system. Numerous studies, both *in vitro* and *in vivo*, have been conducted to characterize the systemic and ocular toxicology profile of H-1337. For complete information on the preclinical studies performed, please see the Investigator's Brochure.

1.4 Dose Rationale

Ocular PK data in rabbits and monkeys confirmed that H-1337 exhibits dose-related effects and can reduce IOP for upwards of 8-12 hours. The clinical doses, treatment period (28 days), and dosing regimen (BID) that are expected to have an acceptable safety profile have been selected based on preclinical toxicology data. The total daily administered dose of H-1337 in human subjects will be approximately 1 mg (or 0.014 mg/kg/day, calculated assuming a 70-kg subject) when administered twice daily in both eyes at the maximal concentration of 0.6%.

1.5 Trial Conduct

This study will be conducted in accordance with current US FDA regulations, International Conference on Harmonization (ICH) guidelines, Good Clinical Practice (GCP) standards, the Declaration of Helsinki, and local ethical and legal requirements.

1.6 Population

Study population will include subjects of either sex and of any race/ethnicity over 18 years of age with a diagnosis of bilateral primary open-angle glaucoma or ocular hypertension.

2 STUDY OBJECTIVES

Primary Objective:

- Evaluate the local ocular and systemic safety of three concentrations of H-1337 in subjects with POAG or ocular hypertension treated daily for up to 28 days.

Secondary Objectives:

- Evaluate the ocular hypotensive efficacy of H-1337.
- Evaluate the systemic pharmacokinetics of H-1337.

3 STUDY DESIGN

3.1 Study Design

The study will evaluate the safety, tolerability, and preliminary efficacy of 3 concentrations of H-1337 and vehicle administered twice daily for 28 days. Up to 100 subjects, naïve to H-1337, will be randomized and dosed for 28 days. The parallel group, double-masked, placebo-controlled study will include the following dosing cohorts:

- H-1337 0.06% (n=20)
- H-1337 0.2% (n = 20)
- H-1337 0.6% (n = 20)
- Control (Vehicle) (n = 20)

Dosing will be BID unilaterally in the study eye for the first 3 days, then BID OU from Day 4 to Day 28.

3.2 Randomization

Randomization will be stratified by Baseline IOP (23 to 26 mmHg and > 26 to 32 mmHg at 8 am). H-1337 and its vehicle will be packaged in identical bottles. An interactive web response system (IWRS) will be used for randomization.

3.3 Maintenance of Randomization Codes

The study will be double-masked to reduce potential bias in clinical assessments. Upon approval of Allysta Pharmaceuticals, Inc., and prior to initiation of the study, an unmasked statistician will generate and maintain the randomization codes which are consistent with the study design. Other study statisticians will be masked to the identity of the treatments until all data have been entered into the database and locked.

In the case of an emergency only, if it is necessary for the investigator (or a treating physician) to know the treatment a subject is receiving, site personnel can complete the subject treatment breaking code procedure in IWRS. The mask should be broken only for safety purposes and only if knowing the drug allocation will have a direct impact on the subject's immediate medical management. If at all possible, the Medical Monitor should be contacted prior to emergency unmasking:

[name]
[contact]
[contact]

If this is not possible and unmasking occurs without prior Medical Monitor approval, the Medical Monitor must be notified within 24 hrs. The circumstances leading to unmasking of each subject are to be promptly communicated via telephone and/or in writing to the sponsor

(or sponsor's designee) and the IRB. Early termination procedures should be conducted for any subject for whom the randomization code is broken.

3.4 Trial Treatment

Subjects will receive one of four dosing arms: H-1337 at concentrations of 0.06%, 0.2%, or 0.6%, or a control vehicle. IP will be administered BID unilaterally in the study eye for the first 3 days, then BID OU from Day 4 to Day 28.

The IWRS will assign a number to subjects who qualify for randomization. The first IP bottle will be dispensed on Day 0 (Baseline) and the second IP bottle will be dispensed to the subject on Day 14. The third IP bottle will serve as a back-up if the subject needs a replacement IP bottle.

3.5 Duration

Each subject's participation will consist of two phases: a screening phase (Screening and Baseline Visits) where subjects will wash out any current ocular hypotensive therapy and a dosing phase, starting on Day 0. If a subject is not on ocular hypotensive therapy, there is no applicable washout period and the Baseline Visit should occur after clearance of clinical laboratories.

A subject could participate in the study for a total of up to approximately 11 weeks. Subjects who meet the applicable inclusion/exclusion criteria at the Screening Visit will discontinue use of any current ocular hypotensive therapy during the washout period. The washout duration will be dependent on the subject's pre-study ocular hypotensive therapy. The table below lists the applicable washout durations for various pre-study ocular hypotensive medications. (Note: This table may not be inclusive of all ocular hypotensive medications. The Medical Monitor should be contacted for further information regarding the washout period of an ocular hypotensive not included in the table.) If the Investigator assesses an acceptable risk, subjects may extend washout up to 49 days to accommodate scheduling.

Table 2 Ocular Hypotensive Medication Washout Schedule

Ocular Hypotensive Generic/Trade Names	Washout period* (between Screening and Baseline Visits)
Muscarinic agonists (e.g., pilocarpine) and Oral or Topical Carbonic Anhydrase Inhibitors (CAI)	≥ 5 days
Beta-adrenoceptor antagonists	≥ 6 weeks
Alpha adrenoceptor agonists	≥ 5 weeks
Prostaglandin analogues, Combination Drugs (use longest wash-out period of individual components)*	≥ 6 weeks

*The washout period of longest duration should be used when the subject is taking multiple ocular hypotensive medications from more than one class. Additional +1 week extended washout permitted to accommodate scheduling considerations.

Following the applicable washout period, the subject will return for applicable inclusion/exclusion evaluations on the Baseline Visit (Day 0). On Day 0, a subject meeting all inclusion/exclusion criteria will be randomized to IP. On Days 0 to 3, only the study eye will be dosed and evaluated for safety. For the remainder of treatment, both eyes will be dosed and evaluated for safety. The study eye is the eye that meets the entry IOP criteria after washout. Should both eyes meet the criteria then the study eye will be defined as the eye with the higher 8 am IOP on Baseline (Day 0). If both eyes have the same 8 am IOP on Baseline (Day 0), the study eye will be the right eye.

Dosing will be initiated in the study eye on Day 0 in the office after the completion of all required examinations. The subject will be dosed for up to 28 days during which time they will be monitored for safety, tolerability, and efficacy assessments according to the Schedule of Study Assessments and Procedures.

The duration of participation for subjects in each stage will be as follows:

Screening Visit: 1 day

Washout Period: up to 6 weeks (+ 1 week) depending on pre-study ocular hypotensive therapy

Treatment Period: 28 days

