7. STATISTICAL ANALYSIS

All statistical analyses and reporting will be performed using the SAS® System Version 9.3 or later.

Unless otherwise specified, continuous variables will be summarized with descriptive statistics (n, mean, median, standard deviation, standard error, minimum, and maximum), and categorical variables will be summarized with counts and percentages.

All data collected in the study database will be presented in the listings.

Definition of Study Eye: The study eye will be the eye that meets the entry intraocular pressure (IOP) criteria after washout. Should both eyes meet the criteria, then the study eye will be defined as the eye with the higher 8 am IOP on Baseline (Day 0). If both eyes have the same 8 am IOP on Baseline (Day 0), the study eye will be the right eye. The study eye will be designated by the investigator. The designation may take into account ocular history as well as IOP criteria.

Definition of Baseline:

For vital signs, PK, BCVA and biomicroscopy baseline is the pre-T0 time point on Day 1. For clinical laboratories and pupil diameter baseline is the Day 0 collection. For IOP and hyperemia baseline is the set of repeated measures at different times during the Day 0 visit. For ophthalmoscopy baseline is the Screening Day.

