7.12 Best-Corrected Visual Acuity

Descriptive statistics of the observed and change from baseline BCVA will be tabulated for each eye by visit and treatment group.

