7.13 Ocular Hyperemia, Biomicroscopy, Ophthalmoscopy and Ocular Symptoms

The observations of ocular hyperemia, biomicroscopy, ophthalmoscopy, and ocular symptoms will be summarized in frequency tables based on the ordinal scales for each measure for each eye by time point and treatment group. In addition, the photographic assessment of ocular hyperemia will be summarized by descriptive statistics (See Appendix 2).

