9.2 Appendix 2. Efficacy Endpoints and Time Points

IOP

Category	Day 0 Visit	Day 1 Visit*	Day 4 Visit*	Days 14 & 28 Visits
Eye subgroups	Study eye Mean of both eyes	Study eye	Study eye	Study eye Mean of both eyes
Analysis variables	IOP & Diurnal IOP	
• IOP• Change in IOP from baseline (Day 0 Visit)*• % change in IOP from baseline (Day 0 Visit)*• Proportion of subjects achieving IOP \leq 18 mmHg	
• IOP• Change in IOP from baseline (Day 0 Visit)• % change in IOP from baseline (Day 0 Visit)• Proportion of subjects achieving IOP \leq 18 mmHg	
• IOP & Diurnal IOP• Change in IOP & Diurnal IOP (Day 0 Visit)• % change in IOP & Diurnal IOP (Day 0 Visit)• Proportion of subjects achieving IOP/Diurnal IOP \leq 18 mmHg
Analysis Time points	
• T_0$T_0 + 1$ hrs$T_0 + 2$ hrs$T_0 + 4$ hrs$T_0 + 8$ hrs$T_0 + 12$ hrs• Diurnal (mean of 5 measurements & mean of 4 measurements excluding $T_0 + 12$ hrs)	T_0	T_0	
• T_0$T_0 + 1$ hrs$T_0 + 2$ hrs$T_0 + 4$ hrs$T_0 + 8$ hrs$T_0 + 12$ hrs• Diurnal (mean of 5 measurements & mean of 4 measurements excluding $T_0 + 12$ hrs)
Treatment Groups/ Comparisons	H-1337 vs. Vehicle	H-1337 vs. Vehicle	H-1337 vs. Vehicle	H-1337 vs. Vehicle

*Note: the non-study eye will not be treated until after T_0 on the Day 4 visit. Day 0 measures will be used as baseline for all time points for the non-study eye.

Conjunctival Hyperemia by Photographic Assessment

Category	Day 0 Visit	Day 4 Visit*	Day 14 Visit	Days 28 Visit
Eye subgroups	Study eye Mean of both eyes	Study eye	Study eye	Study eye Mean of both eyes
Analysis variables	Conjunctival Hyperemia by Photographic Assessment	
HyperemiaChange in Hyperemia from baseline (Day 0 Visit)*	
HyperemiaChange in Hyperemia from baseline (Day 0 Visit)	
HyperemiaChange in Hyperemia from baseline (Day 0 Visit)
Analysis Time points	
Pre-T_0$T_0 + 2$ hrs$T_0 + 4$ hrs$T_0 + 8$ hrs$T_0 + 12$ hrs	
Pre-T_0	
Pre-T_0	
Pre-T_0$T_0 + 2$ hrs$T_0 + 4$ hrs$T_0 + 8$ hrs$T_0 + 12$ hrs
Treatment Groups/ Comparisons	H-1337 vs. Vehicle	H-1337 vs. Vehicle	H-1337 vs. Vehicle	H-1337 vs. Vehicle

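### Protocol 3.5, read literally, leaves the fellow eye ungraded for hyperemia after T0 on Day 0, so 4 of 5 planned Day 28 both-eye changes would have no matched baseline

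*Protocol*

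**What the plan says.** Protocol 3.5 (Duration) states: "On Days 0 to 3, only the study eye will be dosed and evaluated for safety". The next sentence reads: "For the remainder of treatment, both eyes will be dosed and evaluated for safety".

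The schedule has separate hyperemia grading five times on Day 0 (T0, T0 + 2, + 4, + 8 and + 12 h), once before T0 on Days 4 and 14, and five times on Day 28 (pre-T0, then + 2, + 4, + 8 and + 12 h). There is none at Screening or on Day 1. The IP administration row says which eye is dosed; the hyperemia and biomicroscopy rows name no eye.

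SAP section 7 defines the baseline: "For IOP and hyperemia baseline is the set of repeated measures at different times during the Day 0 visit". In SAP Appendix 2, the hyperemia table gives the eye subgroups for Day 0 and Day 28 as "Study eye Mean of both eyes" and lists change from Day 0 as a Day 28 variable. Its footnote adds: "Day 0 measures will be used as baseline for all time points for the non-study eye". SAP 7.13 plans frequency tables for hyperemia and biomicroscopy "for each measure for each eye by time point and treatment group".

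**The concern.** One document limits evaluation on Day 0 to the study eye. The other needs Day 0 values from the eye left out.

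Safety is the primary objective, and the protocol background names conjunctival hyperemia as the most frequent adverse event with topical rho kinase inhibitors. Protocol 7.1 does not require non-clinically significant changes of less than 2 grades to be reported as adverse events, so the grading tables are the main record of mild reddening. Both eyes are dosed from Day 4, so half of the exposed eyes are fellow eyes. A Day 0 grade that was not taken cannot be recovered later.

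**Working it through.** No power or sample-size figure is involved. The check sets the passages side by side and then counts.

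**1. Does 'only' restrict evaluation or just dosing?** The two sentences in 3.5 pair dosing with evaluation, first for one eye and then for both. The contrast makes 'only' apply to both verbs. The first dose follows the T0 + 12 h IOP on Day 0 (Protocol section 5), so every scheduled Day 0 ocular examination is pre-dose. If 'evaluated' meant follow-up of a dosed eye, it would cover almost nothing scheduled on Day 0, yet the sentence names Day 0.

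**2. Which fellow-eye values are protected by other text?**

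| Measure | Protection elsewhere | Result |
|---|---|---|
| IOP, six Day 0 times | Inclusion criterion 4 applies to both eyes at all time points; the procedure is repeated on the other eye | Secured |
| BCVA | The procedure tests the right eye, then the left | Secured on Day 0. The SAP baseline is Day 1, inside the restricted window, but the same procedure applies |
| Pupil diameter | Single pre-T0 value on Day 0, before the study eye is normally known | Effectively secured |
| Hyperemia at T0 | Graded before the IOP reading that selects the study eye | Effectively secured |
| Hyperemia at + 2, + 4, + 8, + 12 h | None: procedure and schedule name no eye | At risk |
| Biomicroscopy at the same Day 0 times and on Day 1 | Weak: the one OU in the procedure follows the mention of pupil dilation and may belong to that | At risk |
| Ophthalmoscopy | Baseline is Screening | Unaffected |

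**3. What the gap does to hyperemia.** The both-eye change at time t is

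(study eye + fellow eye)/2 on Day 28 − (study eye + fellow eye)/2 on Day 0, both at time t.

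It needs four grades. Without the fellow-eye Day 0 grade it is undefined, and the SAP has no imputation rule for hyperemia grades.

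- Day 28 time points: 5.
- Matched fellow-eye baselines under a literal reading: 1 (T0).
- Without a baseline: 5 − 1 = 4.

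The morning dose on Day 28 follows the T0 IOP, so these four are exactly the post-dose times. The one that survives is pre-dose.

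- Fellow eyes: 4 arms × 20 = 80, or 75 to 100 over the stated enrollment range.
- Grades at risk: 80 × 4 = 320, or 300 to 400 over that range.

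**4. What the gap does to biomicroscopy.** Four Day 0 examinations and one Day 1 examination per fellow eye could be missing. SAP 7.13 plans frequency tables here, so the loss is empty cells and not a change score. The Day 1 examination is the SAP's baseline visit: "For vital signs, PK, BCVA and biomicroscopy baseline is the pre-T0 time point on Day 1".

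**5. Is there a substitute hyperemia baseline?** Screening biomicroscopy includes a hyperemia grade but precedes washout, and exclusion criterion 14 accepts hyperemia due to prostaglandin use. The pre-T0 grade on Day 4 is taken before the fellow eye is dosed, but it is a single morning value, and Appendix 2 lists only the study eye at that visit. Neither is time-matched.

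**The case against.** The best reply is that 3.5 describes follow-up of dosed eyes and was never meant to limit baseline examinations. The same section says dosing starts after all required examinations and refers monitoring to the schedule, which restricts no ocular examination to one eye. At each of the four times both eyes already have IOP measured, so an examiner may well grade both. The CRF, which is not part of the documents, may have fields for each eye. This makes the loss less likely, but it does not settle the text: for Day 0 hyperemia after T0, 3.5 remains the only instruction that names an eye.

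The analytical consequence is also limited, and that stands. The hyperemia summaries are descriptive, the both-eye mean appears after baseline only at Day 28, and observed Day 28 grades can still be compared with vehicle without a baseline.

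A reader might infer that fellow-eye and both-eye safety changes in general would lack a baseline. The documents do not support that, as the table under the working shows. The per-eye BCVA plan ("Descriptive statistics of the observed and change from baseline BCVA will be tabulated for each eye by visit and treatment group") is not evidence for it either, because the SAP baseline for BCVA is Day 1 and the procedure tests both eyes.

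A reader might also infer that the dosed-versus-undosed comparison within a subject is lost. It is not: the fellow eye stays undosed until after T0 on Day 4, and biomicroscopy and hyperemia are scheduled before T0 that day.

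**Conclusion.** The conflict is real but narrow. If 3.5 is followed literally, the Day 28 change in hyperemia cannot be computed for the fellow eye, or for the planned mean of both eyes, at 4 of 5 time points, all of them post-dose. Fellow-eye biomicroscopy at the same Day 0 times and on Day 1 could be absent from the per-eye tables. The other ocular measures are not materially affected.

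The figure of about 80 eyes is an upper bound at the planned arm sizes. It assumes that every site adopts the literal reading. It also assumes that the study eye is unknown until the T0 IOP. Where it is known earlier, for example because the corneal exclusions apply to the study eye only, the T0 grade would be at risk too.

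The point should be corrected because the loss would be permanent, it affects a planned analysis under the primary objective, and preventing it costs almost nothing. That the SAP's Day 1 baseline for BCVA and biomicroscopy follows the first study-eye dose is a separate question, and this point does not rest on it.

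**What to change.** Reconcile the passages:

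- In Protocol 3.5, separate dosing from evaluation. Say that only dosing is unilateral on Days 0 to 3, and that both eyes are examined at every scheduled ocular assessment from Day 0 onward.
- Mark the hyperemia and biomicroscopy rows OU in the protocol schedule and in SAP Appendix 1.

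The dosing text itself does not change. The cost is one reworded sentence, the row labels, and a few extra minutes per time point in sittings where both eyes already have IOP measured. A summary of the study eye against the undosed fellow eye before dosing on Day 4 could be added to SAP 7.13, but it is optional and not needed to resolve the conflict.

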3.6 Drug Packaging and Labeling

H-1337 and its vehicle will be packaged in a 5 mL low density polyethylene (LDPE) clear bottle with a dropper nozzle insert delivering a drop volume of 43 µL. The bottles will be packaged in cartons in a format appropriate for the study; both bottles and cartons will be labeled in a format appropriate for the study. Representative labels are as follows:

Bottle label:

Placebo or H-1337 Ophthalmic Solution, 5.0 mL
Use as directed. Refrigerate at 2-8°C until opened.
Caution: New Drug-Limited by Federal (US) Law to
Investigational Use. Allysta Pharmaceuticals, Inc.
Protocol: ALY337-201 Number: #####

Carton label:

Placebo or H-1337 Ophthalmic Solution, 5.0 mL
Protocol Number: ALY337-201
Subject Number: _____
Assignment Number: #####
Store refrigerated at 2-8 °C (36-46°F). Protect
from Freezing. "Caution: New Drug-Limited by
Federal (United States) Law to Investigational
Use". Sponsor: Allysta Pharmaceuticals, Inc.

3.7 Drug Accountability and Storage

All IP required for this study will be provided by Allysta Pharmaceuticals, Inc., or its designee. The recipient will acknowledge receipt of IP, indicating shipment content and condition. Damaged supplies may be replaced upon notification to Allysta Pharmaceuticals, Inc., or its designee. Accurate records of all IP dispensed from and returned to the study site should be maintained and recorded. A study monitor will periodically check the supplies of IP held at the site to verify accountability of all IP. All used and unused IP (non-dispensed) will be returned to Allysta Pharmaceuticals, Inc., or its designee.

IP must be kept in a safe storage area with limited access (e.g., in a locked cabinet). The storage area should be temperature monitored. IP should be stored at controlled refrigerated temperatures from 2°C to 8°C and protected from light. After opening, IP bottles may be stored at room temperature, i.e., 15°C to 25°C. Subjects should be instructed not to leave the IP in their car, near a window, or outdoors where it may be exposed to direct sunlight and/or heat for a prolonged period.

The IP must not be used outside the context of this protocol. Under no circumstances should the investigator or site personnel supply IP to other clinical sites, investigators or subjects, or allow the IP to be used other than as directed by this protocol without prior authorization from Allysta Pharmaceuticals, Inc.

